7.2 NUMBER OF SUBJECTS AND INVESTIGATIONAL SITES

A total of forty (40) subjects will be enrolled at a single US site.

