18. STATISTICAL ANALYSIS PLAN

18.1 STUDY HYPOTHESIS

The primary hypothesis is that the probability of experiencing device-related Serious Adverse Events (SAE) for subjects treated with the investigational device is smaller than the performance goal of 1%. Formally, that hypothesis to be tested are:

H_0 : The expected proportion of subjects with device-related SAE up to Day 30 (p_T) is greater than or equal to the performance goal (PG) of 1.0%.

H_A : The expected proportion of subjects with device-related SAE up to Day 30 (p_T) is less than the performance goal (PG) of 1.0%.

These hypotheses may be symbolically represented as:

$$H_0: p_T \geq PG = 1.0\%$$

$$H_A: p_T < PG = 1.0\%$$

Where p_T is the device-related SAE rate for subjects treated with the investigational device.

If the Bayesian Posterior Probability that $p_T < PG$ is greater than or equal to .975, the alternative hypothesis will be accepted, and it will be concluded that the device meets the performance goal.

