OHSU (unpublished)	X	X	X	Yes
LUMC (ongoing)	X	X	X	Yes
BARWON (ongoing)	X	X	X	Yes

The summary findings are shown below Table 8.

Table 8: Informative Prior Data

Study	# Subjects	Device Related SAEs
Robert Guerri-Fernandez (2018)	40	0
Mellibovsky L, et al (2015)	52	0
OHSU	18	0
LUMC (ongoing)	110*	0*
BARWON (ongoing)	50*	0*
Total	270*	0*

*Anticipated at the time of De Novo submission

These five studies contain or will contain 270 subjects with an anticipated rate of zero subjects experiencing a device-related Serious adverse events. Given there is no variability between these studies, the data are pooled together and collectively constitute the informative prior. To be conservative, the initial assumption will only consider 215 subjects with zero device-related adverse events. The informative prior was constructed as Jeffries prior plus the data in Table 8, that is, Beta(.5 + data, .5 + data).

When there are zero device-related SAEs in 40 prospective subjects, the posterior probability will be .9765 and the device will have been shown to meet the performance goal. Therefore, only if there are zero device-related SAE's will the alternative hypothesis be accepted.

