18.4 TESTING OF PRIMARY SAFETY HYPOTHESES

The primary safety hypothesis will be tested by determining the Bayesian posterior probability that the device-related SAE rate is less (i.e., better) than the performance goal. The Bayesian posterior probability will be calculated by updating historical data with prospective trial data. The Bayesian posterior probability will be calculated through numerical integration with regards to the performance goal of .01. When the Bayesian posterior probability of the conditional device-related SAE rate is higher than .975, the alternative hypothesis will be accepted, and it will be concluded that the device has met the specified performance goal of 1%. As stated above, this will only occur when there are zero out of 40 events.

Supporting analyses will summarize the Bayesian posterior probabilities that the device-related SAE rate is lower than varying reference margins.

95% credible intervals of the device-related SAE rate will also be reported without using an informative prior distribution.

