18.5 MISSING DATA/SENSITIVITY ANALYSIS

Given the short follow-up, there is not expected to be a large amount of missing data. Detailed descriptions of the reason(s) for missingness will be provided for every missing subject and timepoint. Subjects missing data will be multiply imputed using the posterior distribution of the observed data only. Bayesian posterior summarizes will characterize best- and worst-case scenarios as sensitivity to MAR assumption necessary for the imputation model. There will be no imputation for secondary effectiveness endpoints.

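### Section 18.5 plans only best- and worst-case bounds for missing primary outcomes; these cannot show how large a departure from MAR would overturn the conclusion, and a tipping-point analysis between them would

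*Combined protocol and SAP*

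**What the plan says.** The primary test concerns the device-related SAE rate up to Day 30. Section 18.4 states: "The Bayesian posterior probability will be calculated through numerical integration with regards to the performance goal of .01". Section 18.1 gives the success rule: if the posterior probability that the rate is below that goal "is greater than or equal to .975, the alternative hypothesis will be accepted". Section 18.2 describes the prior: "The informative prior was constructed as Jeffries prior plus the data in Table 8, that is, Beta(.5 + data, .5 + data". It sizes the trial on the smaller of two historical counts ("the initial assumption will only consider 215 subjects with zero device-related adverse events"), although the larger total is also given: "These five studies contain or will contain 270 subjects with an anticipated rate of zero subjects experiencing a device-related Serious adverse events". The prospective sample is 40 (section 7.2: "A total of forty (40) subjects will be enrolled at a single US site"). In event counts, section 18.2 says that "only if there are zero device-related SAE's will the alternative hypothesis be accepted".

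Section 18.5 expects little missing data, promises the reasons for each missing subject and timepoint, and imputes missing outcomes from the posterior of the observed data. The sensitivity analysis is one sentence: "Bayesian posterior summarizes will characterize best- and worst-case scenarios as sensitivity to MAR assumption necessary for the imputation model". It neither defines the two cases nor attaches a pass/fail rule to them. It plans no intermediate scenario and does not say how results are combined over imputations.

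**The concern.** The success rule tolerates no event. A scenario that gives every missing subject an event must therefore miss the threshold, and one that gives none an event repeats the design calculation when no event was observed. On which side of .975 each scenario falls is known before any data are seen.

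Missing outcomes are possible: section 10.2 does not replace subjects withdrawn after treatment, and section 10.1 treats anyone who misses the 30-day visit as lost to follow-up. If this happens, the reader of a de novo submission gets one scenario below the threshold and one above it. Nothing planned says how far the missing subjects would have to differ from the observed ones before the conclusion changed. That is the question a sensitivity analysis of MAR should answer.

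**Working it through.** **Inputs.** Performance goal .01 and threshold .975 (sections 18.1 and 18.4); Jeffreys base with 215 or 270 event-free historical subjects (section 18.2); 40 prospective subjects (section 7.2). The number missing, m, is not given, so 1, 2 and 4 are shown as assumptions. Best case is assumed to mean that no missing subject has an event, and worst case that all do.

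**Formula.** With x events among N subjects in prior plus trial, the posterior is Beta(.5 + x, .5 + N − x). Let P(x, N) be its probability below .01.

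**The plan's figure.** N = 215 + 40 = 255 and x = 0 give P = .97649, which matches the stated .9765. With 270, N = 310 and P = .9875.

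**Bounds, no observed event:**

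| Scenario | 215 prior | 270 prior |
|---|---|---|
| Best case, any m | .9765 | .9875 |
| Worst case, m = 1 | .8368 | .8989 |
| Worst case, m = 2 | .5975 | .7142 |
| Worst case, m = 4 | .1736 | .2798 |

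**Conditions on these results.**
- One event reaches .975 only from N = 466 (P(1, 465) = .97492; P(1, 466) = .97515). The documents offer at most 270 + 40 = 310, so the worst case falls short for every m ≥ 1.
- Zero events reach .975 only from N = 250 (P(0, 249) = .97480; P(0, 250) = .97509). In Table 8 the two ongoing studies supply 110 + 50 = 160 of the 270 and are marked as anticipated. The other three supply 40 + 52 + 18 = 110. With those alone, N = 150 and the best case is .918, below the threshold.
- With one observed event and N = 40 in the trial, even the best case is .8368 (215) or .8989 (270).

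**Tipping point.** Let each missing subject have an SAE with probability q, and average the posterior probability over the imputed counts:

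A(q) = Σ Binomial(k; m, q) × P(k, N), summed over k = 0 to m.

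Solve A(q) = .975. For m = 1 this is q = [P(0, N) − .975] / [P(0, N) − P(1, N)]. With 215: (.97649 − .975) / (.97649 − .83683) = .00149 / .13966 = 1.07%. With 270: (.98748 − .975) / (.98748 − .89889) = .01248 / .08859 = 14.1%.

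| Missing | Tipping q, 215 prior | Tipping q, 270 prior |
|---|---|---|
| 1 | 1.07% | 14.1% |
| 2 | 0.53% | 6.8% |
| 4 | 0.27% | 3.3% |

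**How the value is read.** Take one missing subject, no observed event and 215 prior subjects. If the imputation model includes the historical data, the imputed SAE probability is .5 / (.5 + .5 + 215 + 39) = .5 / 255 = 0.20%. That is below 1.07%, and the averaged posterior is .9762. If it uses the 39 observed trial subjects with a Jeffreys prior only, the probability is .5 / 40 = 1.25%. That is above 1.07%, and the averaged posterior is .9747. Section 18.5 does not say which model applies. The tipping value shows how close the result is; the two bounds do not.

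**The case against.** The strongest reply is that section 18.5 promises posterior summaries, not verdicts. Those summaries are informative: with 215 prior subjects the worst case moves from .837 to .598 to .174 for 1, 2 and 4 missing, and the distance between the bounds shows how far the conclusion rests on unobserved subjects. This stands. A reader might infer that the bounds say nothing about MAR, or that the best case passes unconditionally. The documents support neither: the bounds hold without MAR, and the best case depends on no observed event and on at least 250 event-free subjects, many of them still anticipated.

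Second, the worst-case shortfall follows from the openly declared zero-event rule and is not an error in section 18.5. That also stands.

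Third, with no observed event the tipping value depends only on the number missing and the prior size, so it too can be tabulated in advance. It cannot separate a subject last seen well shortly before the final visit from one lost on Day 1. This is correct, and it is why the value needs subject-level information beside it. It still differs from the bounds in kind: it is a probability whose plausibility can be judged.

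Fourth, much is already planned or in place. Section 18.5 promises reasons for missingness, and section 18.7 lists AEs in subjects discontinued early and promises a discussion of possible bias. Section 10.4 keeps data collected before discontinuation. Telehealth visits, a ±10-day window and repeated contact attempts should keep losses low. Nor do the documents say that a missed 30-day visit by itself makes the primary outcome missing. These points limit the exposure, but none supplies an intermediate scenario.

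**Conclusion.** The point holds as a gap in the sensitivity analysis, not as a fault in the bounds or the primary test. With any missing subject the worst case stays below .975 under either prior size. With no observed event and at least 250 event-free subjects in total, the best case stays at or above it. Nothing planned locates the change between them.

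That location matters. For one missing subject it is 1.07% with 215 prior subjects, close to the 1% goal itself, and 14.1% with 270. The first is a fragile result and the second a fairly robust one, yet both have a best case above .975 and a worst case below it.

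The conclusion assumes the usual reading of the two cases, no observed event, 40 subjects in the analysis set, and averaging of the posterior probability over imputations. The documents state neither the case definitions nor the averaging rule.

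**What to change.** In section 18.5:

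1. Define best case and worst case, and keep both as bounds.
2. Add a tipping-point analysis. For the actual number missing and the prior actually achieved, report the smallest SAE probability per missing subject at which the posterior probability, averaged over imputations, falls below .975.
3. State that averaging rule, and whether the imputation posterior includes the historical data.
4. Present the tipping value beside each missing subject's last contact day and status at that contact, together with the reasons for missingness already planned.

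The cost is SAP wording and a few lines of code. Enrolment, visits and the primary test are unchanged. The downside is a little more analysis work and a tipping value that may turn out small, particularly if the prior ends near 215.

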18.6 SECONDARY EFFECTIVENESS ENDPOINTS

The secondary endpoints of this study, following evaluation with the OsteoProbe System, are:

- Follow-up NRS Pain scores take at Procedure, 1-day, and 7-day follow up visits
- BMSi scores at Procedure
- Adverse event through day 30.
- All device-related adverse events through day 30.
- Serious adverse events through day 30; and
- Unanticipated adverse device effects (UADE) through day 30.

Secondary endpoints are described in the Clinical Protocol. Continuous variables will be described by the number of observations, the number of missing observations, means, standard deviations, medians,

Clinical Study Protocol

minimums, and maximum. Responder variables will be described by the number of observations, the number of missing observations, and percentages. Secondary endpoints may be further described through credible intervals or other posterior distribution summaries.

18.7 SAFETY ANALYSES

Assessment of the safety of the investigational device will include an evaluation of the incidence and severity of complications and adverse reactions associated with the treatment.

Adverse event rates will be summarized by type of AE and for specific AEs in two ways: 1) per subject incidence of specific AEs and classes of AEs and 2) by event, summarizing event counts by visit interval over time and in accordance with FDA Guidance (CDRH 2004).¹ device-related events will be summarized by severity and relatedness.

Event listings that include details such as relatedness, severity, onset, and resolution status will be provided for all events and relevant subsets of events such as serious events and related events. Safety evaluations will be performed using the Primary Analysis Set.

The summary tables will show the adverse events (in coded terms), the total number of events, and the number and the percentage of subjects affected ("subject wise evaluation") and stratified by relation to device or procedure and severity. Data of dropouts will not be presented separately, but possible bias will be discussed in the final report.

All AEs will be summarized in listings for the Primary Analysis Set. The following AE listings will be provided:

1. AE Listing 1 All AEs Sorted by Event Type
2. AE Listing 2 All AEs Sorted by Subject
3. AE Listing 3 Serious AEs
4. AE Listing 4 Severe AEs
5. AE Listing 5 Device-related AEs
6. AE Listing 6 Serious device-related AEs
7. AE Listing 8 Other AEs
8. AE Listing 9 AEs among subjects discontinued early
9. AE Listing 10 AEs among subjects who died

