7.10 SUBJECT ENROLLMENT

The point of enrollment occurs when the Investigator delivers the local anesthetic. All enrolled subjects, including those found to be ineligible after consent, will be followed for the next 30 days in accordance with the Schedule of Assessments.

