8. STUDY VISIT PROCEDURES

8.1 VISIT 1: SCREENING/PROCEDURE VISIT

Note: The Screening/Procedure visit may take place over multiple days, but the OsteoProbe procedure must be completed within 7 days of signing the ICF.

Upon successful documentation of informed consent, the subject will be screened to confirm subject eligibility. The screening will include a documentation of demographics, medical history, physical exam with vitals (temperature, blood pressure, pulse and respiratory rate), x-rays to rule out tibial fractures or implants, pregnancy evaluation (for women of childbearing potential only), work status, and concomitant medications.

Upon successful confirmation of subject eligibility, the subject will undergo the following:

Baseline NRS Survey

- The subject will complete a baseline Numerical Rating Scale (NRS) Survey right before initiating the OsteoProbe test procedure

OsteoProbe Test Procedure

- The Investigator will clean the test site and apply a local anesthetic agent prior to performing the OsteoProbe procedure, as outlined in the Procedure Guide, with the assigned device. The Investigator will note the anesthetic agent used, time of delivery and the volume administered in the subject's study records.
- The procedure start time will be recorded as the time of first insertion of the Tip to the bone surface
- The procedure stop time will be recorded as the time the Tip is removed from the skin following the final indentation
- The Investigator will consider the procedure to be successful once the OsteoProbe software displays the BMSi
- If the Investigator cannot complete the procedure for any reason, they should stop the use of the device on this subject and treat the subject per SOC

Post-Procedure (< 60 Minutes)

- The Investigator or delegate will apply a dressing to the test site per SOC
- The Investigator or delegate will record the BMSi Score
- The subject will complete the post-procedure Numerical Rating Scale (NRS) Survey—*this pain survey must be administered prior to performing any adverse event or device deficiency evaluations to prevent information from these assessments biasing the subject's responses.*
- The Investigator or delegate will record adverse events and device deficiencies, if applicable
- The Investigator or delegate will review the suggested post-procedure regimen with the subject per the User Manual
- The Investigator or delegate will perform a review of concomitant medications with the subject

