18.3 STUDY POPULATIONS

18.3.1 Primary Analysis Set

All subjects with a time of procedure start recorded will be included in the Primary Analysis Set. The Primary Analysis Set will be utilized in testing of the primary safety endpoint.

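### The adverse event tables and listings in 18.7 leave out an enrolled subject whose procedure is abandoned after the anesthetic and before the Tip reaches bone

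*Combined protocol and SAP*

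**What the plan says.** Section 18.7 names one population for safety: "Safety evaluations will be performed using the Primary Analysis Set". It repeats this for the listings: "All AEs will be summarized in listings for the Primary Analysis Set". Section 18.3.1 defines that population: "All subjects with a time of procedure start recorded will be included in the Primary Analysis Set". Section 8.1 defines the time in question: "The procedure start time will be recorded as the time of first insertion of the Tip to the bone surface".

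Enrollment comes earlier. Section 7.10 says "The point of enrollment occurs when the Investigator delivers the local anesthetic", and continues: "All enrolled subjects, including those found to be ineligible after consent, will be followed for the next 30 days". Section 14.3.1 starts AE collection at the same moment. Under 14.5 the Clinical Events Committee (CEC) adjudicates every AE.

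The protocol foresees a procedure that is not finished. Section 8.1 says: "If the Investigator cannot complete the procedure for any reason, they should stop the use of the device on this subject". The only other analysis set is the optional per-protocol set in 18.3.2. Section 18.6 lists the AE, SAE and UADE endpoints without naming a set.

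**The concern.** Data collection and reporting start at different points. AEs are collected from the anesthetic onward, but they are tabulated and listed only for subjects in whom the Tip reached bone. The interval between the two is short, but it is not free of risk: 4.1 counts an allergic reaction to the anesthetic among the device- and procedure-related risks. Such a reaction is also a plausible reason to stop. A subject could therefore fall outside the safety tables because of the very event that the tables should show.

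The study exists to characterize safety (5.1), and its secondary objective extends to all safety events (5.2). In a single-arm study of 40 subjects, one omitted subject is visible in a per-subject incidence.

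**Working it through.** **Step 1: follow one subject through the definitions.** Take a subject who receives the anesthetic and is stopped before the Tip touches bone, for a reason other than withdrawal of consent or ineligibility, and who stays in follow-up.

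| Question | Section | Answer |
|---|---|---|
| Enrolled? | 7.10 | Yes, at the anesthetic |
| AEs collected? | 14.3.1 | Yes, from the anesthetic |
| Followed for 30 days? | 7.10 | Yes |
| AEs adjudicated? | 14.5 | Yes |
| Procedure start recorded? | 8.1 | No, the Tip did not reach bone |
| In the Primary Analysis Set? | 18.3.1 | No |
| In the AE tables and listings? | 18.7 | No |
| In the AE endpoints of 18.6? | 18.6 | Not stated |

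**Step 2: size in the AE tables.** Section 7.2 fixes 40 enrolled subjects. The number abandoned is not given, so I assume 1 or 2. I also assume that each of them has the AE in question and that no other subject does.

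- One subject: the table shows 0/(40 − 1) = 0/39. On all enrolled subjects it is 1/40 = 2.5%.
- Two subjects: the table shows 0/38. On all enrolled subjects it is 2/40 = 5.0%.

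The opposite effect of a wider set is small. If the AE occurs in one measured subject and the one abandoned subject is free of it, the rate moves from 1/39 = 2.56% to 1/40 = 2.50%.

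**Step 3: effect on the primary test.** Inputs from 18.1 and 18.2: a Jeffreys prior, Beta(0.5, 0.5); prior data of 0 events in 215 subjects; a performance goal of 1%; a threshold of 0.975. With x events in n subjects, the posterior is Beta(0.5 + x, 0.5 + 215 + n − x), and the test uses P(p < 0.01).

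The plan's own figure comes first. For 0/40 the posterior is Beta(0.5, 255.5), which gives 0.97649. This matches the stated .9765.

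| Situation | Events/n | P(p < 0.01) | Result |
|---|---|---|---|
| Plan | 0/40 | 0.97649 | pass |
| One abandoned, no related SAE | 0/39 | 0.97622 | pass |
| Two abandoned, no related SAE | 0/38 | 0.97594 | pass |
| One abandoned with a device-related SAE, left out | 0/39 | 0.97622 | pass |
| Same subject counted | 1/40 | 0.83683 | fail |

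With zero events, the smallest n that still passes is 35. With the anticipated prior of 270 subjects in Table 8, the last two rows become 0.98734 and 0.89889, again a pass and a fail.

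**The case against.** **A device-exposed safety set is coherent.** Section 6.3 speaks of subjects evaluated with the device, 18.1 of subjects treated with it, and 18.7 opens with the safety of the device. This stands for the primary test, where the bone-contact set should stay. It does not justify leaving collected AEs out of every table and listing, because 4.1 treats an anesthetic reaction as a risk of the device and procedure.

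**Other text may bring these AEs back in.** Section 18.7 also promises event listings for all events, but the same section then ties the listings to the Primary Analysis Set. Section 10.4 brings in data of subjects who withdraw, are discontinued by the investigator or are lost to follow-up. That may cover an abandoned subject who is then discontinued, although 10.4 names no set. It does not cover one who stays in follow-up.

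**Stronger readings.** A reader might infer more than the documents support:

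- *The primary result is unsafe.* The contrast of 0.837 and 0.976 needs three things in one subject: abandonment before bone contact, an SAE, and adjudication of that SAE as device-related. Any single counted event fails a zero-event rule, so the contrast reflects that rule. It does not measure the gap in the AE tables.
- *There is no rule for procedure-related SAEs.* Section 14.2.2 includes the procedure in its relatedness scale, and 14.5 adjudicates on the same combined basis. The phrase "stratified by relation to device or procedure and severity" in 18.7 can be read the same way. At most, 6.3 lacks a cross-reference.
- *Subjects with a skin puncture but no bone contact are lost.* Section 8.1 refers to the Procedure Guide for the steps, and the Guide is not among the documents. Whether such a stage occurs, and how its time is recorded, cannot be settled here.

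**Conclusion.** The point holds as a gap between the point from which AEs are collected and the set in which they are reported. As written, the 18.7 tables and listings omit the AEs of an enrolled subject who is stopped after the anesthetic and before bone contact and who stays in follow-up.

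The size is small. The documents give no rate, and 0 to 2 of 40 subjects is an assumption. Section 7.4 already excludes known anesthetic allergy, needle phobia and soft tissue that precludes use of the device, which makes the case rarer. For one such subject with an AE, the effect is 0/39 against 1/40.

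A reader might infer that these AEs are lost or go unreported to the sponsor. The documents do not support that: collection, reporting and adjudication all run from enrollment. The primary conclusion is likewise unchanged for 0 to 2 abandoned subjects, unless one of them has an SAE adjudicated as device-related.

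The change is still worth making. It costs almost nothing, and it removes a selective omission from a study whose objective is to characterize safety.

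**What to change.** 1. In 18.7, base the AE tables and listings on all enrolled subjects, meaning those who received the local anesthetic. In 18.6, state that the AE, SAE and UADE endpoints use the same set. At minimum, add a listing of AEs for enrolled subjects outside the Primary Analysis Set.
2. Keep the 18.3.1 set for the primary test. A sensitivity posterior on all enrolled subjects is optional. Counting one or two event-free subjects who were never measured raises the posterior only slightly, in the device's favor: from 0.97594 (0/38) to 0.97649 (0/40), a difference of 0.00055. It also fits the prior less well, because 18.2 selected studies in which the procedure was carried out.
3. As a separate minor point, reconcile 7.8 and 10.2 with 7.10. A subject who leaves, or is found ineligible, after the anesthetic but before the procedure is a screen failure under the former and an enrolled subject under the latter.

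The cost is wording in the SAP and protocol. No new data are needed. The downside is that a few subjects never measured with the device enter the AE denominators.
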